14.3. Scoring for QLQ-C30 version 3.0

Table 4 - Scoring for QLQ-C30 version 3.0

	Scale	Number of items	Item range*	Version 3.0 Item numbers	Function scales
Global health status / OoL					
Global health status/QoL (revised) [†]	QL2	2	6	29, 30	
Functional scales					
Physical functioning (revised) [†]	PF2	5	3	1 to 5	F
Role functioning (revised) [†]	RF2	2	3	6, 7	F
Emotional functioning	EF	4	3	21 to 24	F
Cognitive functioning	CF	2	3	20, 25	F
Social functioning	SF	2	3	26, 27	F
Symptom scales / items					
Fatigue	FA	3	3	10, 12, 18	
Nausea and vomiting	NV	2	3	14, 15	
Pain	PA	2	3	9, 19	
Dyspnoea	DY	1	3	8	
Insomnia	SL	1	3	11	
Appetite loss	AP	1	3	13	
Constipation	CO	1	3	16	
Diarrhoea	DI	1	3	17	
Financial difficulties	FI	1	3	28	

Statistical Execution Plan, Version 1.0 Date Issued: 14MAY2021

4. Subscale Scoring for the FACT-B

Subscale	Item	Reverse?	Item response	Item Score	
PHYSICAL WELL	GP1	Yes	x	4 - x	
BEING	GP2	Yes	x	4 - x	
(PWB)	GP3	Yes	x	4 - x	
	GP4	Yes	x	4 - x	
	GP5	Yes	x	4 - x	
	GP6	Yes	x	4 - x	
-	GP7	Yes	x	4 - x	_
			Total		
			×7 Divide by number items answered		= PWB subscale score
SOCIAL/FAMILY WFLI	GS1	No	x	x	
BEING	GS2	No	x	x	
(SWB)	GS3	No	x	x	
	GS4	No	x	x	
	GS5	No	x	x	
	GS6	No	x	x	
-	GS7	No	x	x	_
			Total		
			×7 Divide by number items answered		= SWB subscale score
EMOTIONAL WELL	GE1	Yes	x	4 - x	
BEING	GE2	No	x	x	
(EWB)	GE3	Yes	x	4 - x	
	GE4	Yes	x	4 - x	
	GE5	Yes	x	4 - x	
-	GE6	Yes	x	4 - x	_
			Total ×6		
			Divide by number items answered		= EWB subscale score

Table 5 - Subscale Scoring for the FACT-B

Subscale	Item	Reverse?	Item response	Item	
BREAST	Item		item response		
CANCER	B1	Yes	x	4-x	
SUBSCALE	B2	Yes	x	4 - x	
(BC3)	В3	Yes	x	4 - x	
	B4	No	x	x	
	В5	Yes	x	4-x	
	B6	Yes	x	4 - x	
	В7	Yes	x	4 - x	
	B8	Yes	х	4 - x	
	В9	No	х	x	
	P2	Yes	х	4 - x	_
			Total		
			×10		
			Divide by number items answered		=BC subscale score
FUNCTIONAL WELL-BEING	GF1	No	x	x	
(FWB)	GF2	No	x	x	
	GF3	No	x	x	
	GF4	No	x	x	
	GF5	No	x	x	
	GF6	No	x	x	
	GF7	No	x	x	_
			Total		
			×7		
			Divide by number		
			items answered		= FWB subscale score

Polyphor Ltd POL6326-009 **Subscale Scoring for the FACT-B (cont.)**

14.5. Algorithm for the best response determination according to RECIST v1.1 guidelines, as assessed by the local Investigator's review

- a) Patients need to have two consecutive assessments of PR or CR to be a responder. PR or CR must be confirmed by 2 consecutive tumor evaluations spaced at least 4 weeks (28 days) apart.

review. The order used to determine the First Time Point response is CR>PR>SD>PD, ignoring visits with missing tumor assessments.

- c) The Confirmed Response is determined based on all overall tumor assessments.
- d) Determine the first time point response as the first assessment of the non-confirmed best response (CR > PR > SD > PD) for a patient, then take the first occurrence of the non-confirmed best response and look at the subsequent assessments within the considered period (Results based upon scans performed after start of new anti-cancer therapy will be excluded for analysis derivations) using the following rules.

	Overall respo in eCRF by in	nse entered vestigator	
Case	First Time Point Response (TPR)**	Subsequent Time Point Response (TPR)	Confirmed Response (Best Response)*
1	CR	CR	CR (if assessments at least 4 weeks (28 days) apart).
			(note: sequences of CR NE CR, CR NE NE CR, or CR NE NE NE CR would be considered as confirmed CR)
2	CR	PR	SD, PD or PR
			If CR truly met at first timepoint, any subsequent assessment of PR should make the disease PD at that point. That is, neither a PR nor SD may follow CR
			Therefore, SD, if CR assessment >=6 weeks (+/-7 days), i.e. 35 days after date of randomization (i.e. date of assessment date of randomiz ation \geq 35 days), otherwise PD.
			However, confirmed response may be PR if subsequent scans suggest small lesions were still present at first assessment (in which case first assessment of CR should be changed to PR) *
			(if assessments at least 4 weeks (28 days) apart).
3	CR	SD	SD or PD
			SD, if CR or SD assessment $\geq =6$ weeks (+/-7 days), i.e. 35 days after date of randomization,
			otherwise PD
4	CR	PD	SD or PD
			SD, if CR assessment >=6 weeks (+/-7 days), i.e. 35 days after date of randomization,
			otherwise PD

	Overall respo in eCRF by ir	nse entered vestigator	
Case	First Time Point Response (TPR)**	Subsequent Time Point Response (TPR)	Confirmed Response (Best Response)*
5	CR	NE**	SD or NE
			SD, if CR assessment >=6 weeks (+/-7 days), i.e. 35 days after date of randomization otherwise NE
6	PR	CR	PR (if assessments at least 4 weeks (28 days) apart).
7	PR	PR	PR (if assessments at least 4 weeks (28 days) apart).
8	PR	SD (3) **	SD
9	PR	PD	SD or PD
			SD, if PR assessment >=6 weeks (+/-7 days), i.e. 35 days after date of randomization,
			otherwise PD
10	PR	NE**	SD or NE
			SD, if PR assessment >=6 weeks (+/-7 days), i.e. 35 days after date of randomization,
			otherwise NE
11	SD	SD	SD
12	SD	PD	SD or PD
			SD, if SD assessment >=6 weeks (+/-7 days), i.e. 35 days after date of randomization,
			otherwise PD
13	SD	NE	SD or NE
			SD, if SD assessment >=6 weeks (+/-7 days), i.e. 35 days after date of randomization,
			otherwise NE
14	CR, PR, SD	-	SD or NE
			SD, if assessment >=6 weeks (+/-7 days), i.e. 35 days after date of randomization and does not qualify for CR or PR,
			otherwise NE.
15	PD	No further	PD. Ignore all assessments after initial overall response of PD.

	Overall response entered in eCRF by investigator		
Case	First Time Point Response (TPR)**	Subsequent Time Point Response (TPR)	Confirmed Response (Best Response)*
16	NE	NE	NE Where all assessments are Not evaluable
17	NE	-	NE

* A Best Response of SD can only be made after the subject is on-study for a minimum of six (6) weeks (42 days) +/- seven (7) days, for a minimum time on-study of thirty-five (35) days. If the subject is on-study less than six (6) weeks (42 days) +/- seven (7) days or thirty-five (35) days, any tumor assessment indicating Stable Disease before this time period will have a Best Response of NE unless PD is identified.

** For this study, up to three (3) intervening NEs will be allowed between CRs or PRs but only one (1) intervening SD is allowed between PRs. Subsequent documentation of CR may provide confirmation of a previously identified CR for subjects where the intervening integrated responses, up to three (3), were NE. Subsequent documentation of PR may provide confirmation of a previously identified PR for subjects where the intervening integrated responses, up to three (3), were NE. If the post-NE TPR confirms the CR (or PR) then the Confirmed Response will be CR (or PR). For example, CR NE CR = confirmed CR, CR NE NE CR = confirmed CR, or CR NE NE NE CR = confirmed CR ; PR NE PR = confirmed PR, PR NE NE PR = confirmed PR, or PR NE NE NE PR = confirmed PR ; CR SD CR \neq confirmed CR ; PR SD PR = confirmed PR. Note: in the following scenario, PR SD NE PR, the second PR is not a confirmed PR.

(1) TPR is SD if the increase from the first to the second assessment does not qualify for PD.

The confirmed response (best response) is defined when all Overall response assessments have been reviewed.

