12. STATISTICS

12.1 General Statistical Methods

This section outlines the general study design, study endpoints, and statistical analysis strategy for the study. If, after the study has begun, changes are made to primary and/or key secondary hypotheses, or the statistical methods related to those hypotheses, then the protocol will be amended (consistent with ICH Guideline E9). Changes to exploratory or nonconfirmatory analyses made after the protocol has been finalized, along with an explanation as to when and why they occurred, will be listed in the Clinical Study Report (CSR). Post hoc exploratory analyses will be clearly identified in the CSR. Full details will be in the Statistical Analysis Plan (SAP). Any deviations from the statistical plan will be described and justified in a protocol amendment and/or in the CSR.

All statistical analyses will be carried out using Statistical Analysis System (SAS) version 9.3 (or later). The SAP will be written and finalized prior to the first patient randomized. The SAP will provide a detailed and expanded description of the statistical methods outlined in this protocol. Additional analyses, such as in important subgroups, will be described.

The data from this study will serve a dual purpose:

- (i) To provide efficacy and safety data in the Overall Population, who receive study medication as 2nd to 5th line of therapy, for regulatory submissions in the EU and jurisdictions in which the 2nd line + eribulin label applies.
- (ii) To provide efficacy and safety data in the 3rd line + population who receive study medication as 3rd to 5th line of therapy, for regulatory submissions in the US and jurisdictions in which the 3rd line + eribulin label applies.

For the Overall Population, the critical efficacy endpoints shall be PFS and OS. The formal analysis of PFS is planned once 346 PFS events have accrued and is expected to be conducted when all randomized patients have been followed for a minimum of 12 months. At the time of the PFS analysis, an interim analysis of OS will be performed, and a final analysis of OS will take place once all randomized patients have been followed for a minimum of 24 months.

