Table 7 (Section 8.2.2) provides a summary of the overall response calculation that is to be used at each response assessment timepoint specified in the Study Schedule for patients who have measurable disease at baseline. When patients have non-measurable (i.e. non-target) disease only, Table 8 (Section 8.2.2) is to be used.

Missing Assessments and Inevaluable Designation

When no imaging/measurement is done at all at a particular timepoint, the patient is not evaluable (NE) at that timepoint. If only a subset of lesion measurements is made at an assessment, usually the case is also considered NE at that timepoint, unless a convincing argument can be made that the contribution of the individual missing lesion(s) would not change the assigned timepoint response. This would be most likely to happen in the case of PD. For example, if a patient had a baseline sum of 50 mm with three measured lesions and at follow-up only two lesions were assessed, but those gave a sum of 80 mm, the patient will have achieved PD status, regardless of the contribution of the missing lesion.

Best Overall Response where Confirmation of CR or PR Required

The best overall response is determined once all the data for the patient is known.

Complete or partial responses may be claimed only if the criteria for each are met at a subsequent timepoint as specified in the protocol (i.e. at least 4 weeks later). In this circumstance, the best overall response can be interpreted as shown in Table 17.

Table 17 Best overall response when confirmation of CR and PR required

Overall Response at first timepoint	Overall Response at subsequent timepoint (i.e. at least 4 weeks after first timepoint)	Best Overall Response
CR	CR	CR
CR	PR	SD, PD or PR ^a
CR	SD	SD provided minimum criteria for SD duration met, otherwise, PD
CR	PD	SD provided minimum criteria for SD duration met, otherwise, PD
CR	NE	SD provided minimum criteria for SD duration met, otherwise, NE
PR	CR	PR

Protocol No.: POL6326-009

Version 3.0

Overall Response at first timepoint	Overall Response at subsequent timepoint (i.e. at least 4 weeks after first timepoint)	Best Overall Response
PR	PR	PR
PR	SD	SD
PR	PD	SD provided minimum criteria for SD duration met, otherwise, PD
PR	NE	SD provided minimum criteria for SD duration met, otherwise, NE
NE	NE	NE

CR: complete response; PD: progressive disease; NE: not evaluable; PR: partial response; SD: stable disease

Source: (55)

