8.1.2. Objective Response Rate

Objective response rate (ORR), defined as the proportion of patients with a confirmed complete response (CR) or a confirmed partial response (PR) according to RECIST v1.1 based upon the best response assessed, is a co-primary efficacy endpoint. The alpha allocation will be 0.001 2-sided. As described in section 8, patients will be evaluated for tumor response according to RECIST v1.1 for confirmed CR, confirmed PR, SD, or PD based on blinded, central review of CT/MRI scans. Response will be based on the IRC assessment with a supportive analysis based on the local Investigator's review. Following initial documentation of an objective response, a confirmatory CT/MRI scan will be performed at least 4 weeks later. Results based upon scans performed after start of new anti-cancer therapy will be excluded for analysis derivations.

For the secondary Efficacy Endpoints, the confirmed responses (best responses) determined from Overall responses based on the local investigator's review are not entered in the eCRF and will be derived from the algorithm described in Appendix 14.5.

These data from the CT/MRI scans will be presented in listings; listings for tumor assessment (target, non-target lesions, new lesions, sum of diameters, assessment of disease based on MRI and bone scan). Furthermore, the tumor assessments by the IRC will also be listed.

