- For this study, up to three (3) intervening NEs will be allowed to confirm a CR or PR. Subsequent documentation of a CR may provide confirmation of a previously identified CR with up to three (3) intervening non- evaluable (NE) assessments (e.g. CR NE CR, CR NE NE NE OR, or CR NE NE NE CR). Similarly, subsequent documentation of a PR may provide confirmation of a previously identified PR with up to three (3) intervening NEs (e.g., PR NE PR, PR NE NE PR, or PR NE NE NE NE PR). However, only one (1) intervening SD will be allowed between PRs for confirmation (i.e., PR SD PR).
- Listing of patients with clinically significant abnormalities in vital signs has been removed.
- All AESIs and only the non-overlapping categories for AEPIs will be summarized by treatment arm, MedDRA SOC, Preferred term, and toxicity grade.
- Prior anticancer therapies will not be summarized as regimens since regimens are not identified in eCRF. Individual therapies instead of regimens will be reported.
- Subgroups have been updated in the exploratory efficacy endpoints, section 8.5.
- COVID section added
- Medication errors will not be reported by MedDRA. Instead, they will be reported by medication error event overall and at each visit.

13. References

- Ellis S, Carroll KJ and Pemberton K. Analysis of Duration of Response in Oncology Trials. Contemporary Clinical Trials, 2008; 29: 456-465.
- Carroll, KJ. Back to basics: explaining sample size in outcome trials, are statisticians doing a thorough job? Pharm Stats, 2009; 8: 333–345.
- Dixon D and Simon R. Bayesian Subset Analysis. Biometrics, 1991; 47:871-881.
- MedDRA Dictionary (https://www.meddra.org/)
- NCI CTCAE Grade
 https://ctep.cancer.gov/protocolDevelopment/electronic_applications/ctc.htm

- Sampson HA. Second Symposium on the Definition and Management of Anaphylaxis: Summary Report—Second National Institute of Allergy and Infectious Disease/Food Allergy and Anaphylaxis Network Symposium. Annals of Emergency Medicine. 2006;47(4):373-80.
- FDA 2009. Guidance for industry. Drug-induced livery injury: premarketing clinical evaluation.

 $\underline{http://www.fda.gov/downloads/Drugs/GuidanceComplianceRegulatoryInformation/Guidances/UCM174090.pdf}$

14. Appendices

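### The plan gives two rules for confirming a response, and does not say whether the looser one applies to the co-primary IRC ORR

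*SAP*

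**What the plan says.** **Investigator algorithm (SAP Appendix 14.5).** Step (a) reads "Patients need to have two consecutive assessments of PR or CR to be a responder", and goes on to require that the two evaluations be at least 28 days apart. The footnote to the table says "up to three (3) intervening NEs will be allowed between CRs or PRs but only one (1) intervening SD is allowed" between PRs, and its worked examples include "PR SD PR = confirmed PR". Case 1 likewise accepts CR, up to three NEs, then CR. SAP 8.1.2 and 8.4.2 use this appendix for investigator-assessed response, which SAP 8.4 tests at a nominal 0.05 outside Type I error control.

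**Co-primary endpoint (SAP 8.1.2 and 8.1.3).** "Response will be based on the IRC assessment with a supportive analysis based on the" investigator's review. "The alpha allocation will be 0.001 2-sided". For confirmation of an IRC response, these sections give RECIST v1.1 and a repeat scan at least 4 weeks later, and nothing on intervening NE or SD assessments.

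**Changes from plan (SAP section 12).** Among the changes from the protocol and from SAP version 1.4 is that "up to three (3) intervening NEs will be allowed to confirm a CR or PR", with one SD allowed between PRs. The bullet is worded for the study and names neither the IRC nor the investigator.

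**Protocol.** Appendix 3 says "Complete or partial responses may be claimed only if the criteria for each are met at a subsequent timepoint as specified in the protocol", at least 4 weeks later. Table 17 takes assessments in pairs: PR then SD gives SD, and PR then NE gives SD or NE. Section 12.1 says that if "changes are made to primary and/or key secondary hypotheses, or the statistical methods related to those hypotheses, then the protocol will be amended". Section 12.5 allows deviations to be documented and justified in an amendment, the final SAP or the trial report, as appropriate.

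**The concern.** Confirmation decides who counts as a responder, so it is part of the endpoint definition. Two programmers could both follow the plan and report different investigator response rates. Time to response and duration of response would differ too, because SAP 8.4.5 and 8.4.6 analyse confirmed responders only.

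For the IRC ORR the difficulty is an unanswered question. Section 12 can be read as covering every response derivation in the study, or as a summary of the investigator algorithm in 14.5, and sections 8.1.2 and 8.1.3 do not settle which. The ORR result does more than decide its own test. In the scheme in SAP 14.2 it sets the interim OS alpha at 0.002 or 0.001, and it moves the final OS alpha by 0.001 in the branches where interim OS is positive. The rule should be fixed before the ORR analysis is run.

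**Working it through.** **1. The plan's own figure.** The 3rd line+ error budget with no recycling is ORR 0.001 + PFS 0.040 + interim OS 0.001 + final OS 0.008 = 0.050, as stated in SAP 8.3. The confirmation rule does not change this sum. The plan gives no power or sample size for ORR, so there is no ORR design figure to reproduce.

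**2. The two rules applied to the same scan sequences.** Adjacent evaluations are taken to be at least 28 days apart.

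| Sequence | Step (a) | Footnote |
|---|---|---|
| PR, PR | responder | responder |
| PR, SD, PR | not | responder |
| PR, NE, PR | not | responder |
| PR, NE, NE, PR | not | responder |
| PR, NE, NE, NE, PR | not | responder |
| CR, NE, NE, NE, CR | not | responder |
| PR, NE, NE, NE, NE, PR | not | not |
| PR, SD, NE, PR | not | not |
| CR, SD, CR | not | not |

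Five of the nine change status.

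**3. Comparison with the protocol.** Table 17 gives SD for PR then SD and makes no exception for a later PR, so accepting PR, SD, PR departs from it. For NEs the comparison is less firm. The text above the table asks for a subsequent timepoint without saying consecutive, and the table has no rows for three assessments.

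**4. How late a confirmation can come.** Three NEs between two responses span four scan intervals. At 6-weekly scans that is 4 × 6 = 24 weeks. The ORR analysis requires a minimum follow-up of 6 months.

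**5. Sensitivity at the 0.001 threshold (illustration only).** Assumption: 85% of 160 patients per arm have measurable disease, so 0.85 × 160 = 136. The range 130 to 160 is also shown. Control counts lie near the 9–12% eribulin ORR quoted in protocol 2.2. The test is a two-sided Fisher exact test.

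| Per arm | Control responders | Combination responders | p |
|---|---|---|---|
| 136 | 14 | 35 / 36 | 0.0014 / 0.0009 |
| 160 | 14 | 36 / 37 | 0.00107 / 0.00067 |
| 160 | 19 | 43 / 44 | 0.00103 / 0.00066 |
| 130 | 12 | 32 / 33 | 0.00146 / 0.00089 |
| 130 | 16 | 38 / 39 | 0.00119 / 0.00074 |

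In each row one more responder crosses 0.001. The counts were chosen at the boundary, and the planned test is a stratified exact logistic regression. The table therefore shows what one reclassified patient could do in a close result, not how likely that is.

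**The case against.** The strongest reply is that this is a matter of wording in a secondary endpoint. Step (a) states the general rule, and the table marks its exceptions openly: case 1 carries a note, cases 5, 8 and 10 carry the footnote mark, and the footnote gives worked examples. A careful programmer would probably follow the exceptions. That lowers the risk, but step (a) as it stands still excludes sequences that the footnote includes.

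A reader might infer that the conflict inside 14.5 makes the ORR tested at 0.001 countable in two ways. The documents do not support that. Appendix 14.5 is for the investigator's review, and the 0.001 test uses the IRC. The only link is the section 12 bullet, whose scope is unclear.

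A reader might also infer that the whole tolerance contradicts Table 17, or that it was introduced improperly. The first holds for PR, SD, PR but is not established for NEs. On the second, section 12 discloses the change, and protocol 12.5 permits documentation in the final SAP, although it also asks for a justification and section 12 gives none for this item. The amendment duty in 12.1 arises only if the rule governs the IRC ORR.

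Nor is there evidence of bias toward one arm: the rule is the same in both, and the IRC is blinded. If ORR fails, PFS is still tested at 0.040.

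**Conclusion.** The concern holds in a limited form. Step (a) of SAP 14.5 conflicts with case 1 and the footnote of the same appendix, so investigator ORR, time to response and duration of response are not uniquely defined. Accepting PR, SD, PR departs from protocol Table 17. Whether the section 12 tolerance applies to the co-primary IRC ORR is not stated; if it does, protocol 12.1 calls for an amendment. The SAP, issued 14 May 2021, cites protocol version 3.0 of 15 July 2019, and the documents show no later amendment.

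The effect on the ORR cannot be sized, because the documents do not say how often an intervening SD or NE will occur. The switch from p=0.0014 to 0.0009 rests on an assumed 136 patients per arm, on counts picked at the boundary, and on a Fisher test in place of the planned model. No alpha or sample size in the plan changes.

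**What to change.** - In SAP 8.1.2 and 8.1.3, state the confirmation rule for the IRC ORR, and put the same rule in 14.5 for the investigator ORR. Spell out how an intervening SD is handled and give a maximum number of intervening NEs. A phrase such as next evaluable scan would not do, because it would accept any number of NEs.
- Keep the protocol-consistent rule for the primary ORR: a PR followed by SD is not confirmed by a later PR. Run the tolerant rule (PR, SD, PR and up to three NEs) as a named sensitivity analysis. If the sponsor prefers the tolerant rule as primary, amend the protocol with a justification before the ORR analysis.
- Reword step (a), case 8, the footnote and the section 12 bullet to match, and name the reader to whom each applies.

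The cost is SAP wording and one extra derivation, and the reported ORR may fall slightly. The amendment route adds a protocol amendment.

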A lesion identified in an anatomical location that was not scanned at baseline is considered a new lesion and will indicate disease progression. An example of this is the patient who has visceral disease at baseline and while on study has a CT or MRI brain ordered which reveals metastases. The patient's brain metastases are considered to be evidence of PD even if he/she did not have brain imaging at baseline.

If a new lesion is equivocal, for example because of its small size, continued therapy and follow-up evaluation will clarify if it represents truly new disease. If repeat scans confirm there is definitely a new lesion, then progression should be declared using the date of the initial scan.

While 18-fluoro-deoxyglucose positron emission tomography (FDG-PET) response assessments need additional study, it is sometimes reasonable to incorporate the use of FDG-PET scanning to complement CT scanning in assessment of progression (particularly possible 'new' disease). New lesions on the basis of FDG-PET imaging can be identified according to the following algorithm:

- Negative FDG-PET at baseline, with a positive FDG-PET at follow-up is a sign of PD based on a new lesion.
- No FDG-PET at baseline and a positive FDG-PET at follow-up:

If the positive FDG-PET at follow-up corresponds to a new site of disease confirmed by CT, this is PD.

If the positive FDG-PET at follow-up is not confirmed as a new site of disease on CT, additional follow-up CT scans are needed to determine if there is truly progression occurring at that site (if so, the date of PD will be the date of the initial abnormal FDG-PET scan).

If the positive FDG-PET at follow-up corresponds to a pre-existing site of disease on CT that is not progressing on the basis of the anatomic images, this is not PD.

Evaluation of Best Overall Response

The best overall response is the best response recorded from the start of the study treatment until the end of treatment taking into account any requirement for confirmation. The patient's best overall response assignment will depend on the findings of both target and non-target

¹ A 'positive' FDG-PET scan lesion means one which is FDG avid with an uptake greater than twice that of the surrounding tissue on the attenuation corrected image.

Protocol No.: POL6326-009

Version 3.0

disease and will also take into consideration the appearance of new lesions. Furthermore, it will require confirmation as outlined in Section 8.2.2.

Timepoint Response

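### On the available text, SAP 14.5 step (d) looks only forward from the first CR, so an investigator PR that is already confirmed can be recorded as SD

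*SAP*

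**What the plan says.** SAP 8.1.2 and 8.4.2 state that the investigator's confirmed best response is not collected in the eCRF and is derived by the algorithm in Appendix 14.5. The parts of that appendix that matter here are:

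- Rule (a): a responder needs two consecutive assessments of PR or CR, at least 28 days apart.
- Rule (b), of which only the end is available: the order for choosing the first time point response is CR, PR, SD, PD.
- Rule (c): "The Confirmed Response is determined based on all overall tumor assessments".
- Step (d): find the best unconfirmed response in that order, "then take the first occurrence of the non-confirmed best response and look at the subsequent assessments within the considered period".
- Table: case 6 (PR then CR) and case 7 (PR then PR) give PR. Case 3 (CR then SD), case 4 (CR then PD) and case 5 (CR then NE) give SD once the 35-day condition is met.
- Case 14, no later assessment: SD if the assessment is at least "35 days after date of randomization and does not qualify for CR or PR", otherwise NE.
- Footnote **: up to three intervening NEs are allowed between CRs or PRs, but "only one (1) intervening SD is allowed between PRs".
- Closing sentence: "The confirmed response (best response) is defined when all Overall response assessments have been reviewed".

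Protocol Appendix 3 defines best overall response as the "best response recorded from the start of the study treatment until the end of treatment taking into account any requirement for confirmation". It adds: "The best overall response is determined once all the data for the patient is known". Its Table 17 gives PR both for PR then CR and for PR then PR.

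**The concern.** Step (d) is the only operating instruction in the appendix: it fixes where to start and which way to look. If a patient has any CR, the search starts there, and a PR confirmed beforehand is not considered. A patient whose PR was confirmed and who then improved to an unconfirmed CR can end in a worse category than a patient who never went beyond PR.

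A programmer who follows step (d) literally and one who follows rules (a) and (c) and case 6 would produce different responder lists from the same data. The list feeds investigator-assessed ORR. It also decides who enters time to response and duration of response, because both are restricted to patients with a confirmed CR or PR (SAP 8.4.2, 8.4.5, 8.4.6). CBR (SAP 8.4.3) changes when the resulting SD lasts less than 182 days.

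**Working it through.** There is no plan figure to reproduce. The check applies the rules to response sequences.

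**Why case 6 cannot be reached.** Case 6 needs PR as the starting response and CR as a later one. Step (d) starts at the highest response present, and CR ranks above PR. If a CR exists, the start is that CR, so the start can be PR only when there is no CR. The two requirements of case 6 exclude each other.

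**Inputs for the sequences.** Scans every 42 days from randomization (SAP 3.1), so all are at least 35 days after randomization and at least 28 days apart. Assessments after PD are ignored (case 15).

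| Sequence | Step (d) starts at | Case | Step (d) gives | Rules (a) and (c) with cases 1, 6, 7 and footnote ** give |
|---|---|---|---|---|
| PR PR PD | first PR | 7 | PR | PR |
| PR CR PD | CR | 4 | SD | PR |
| PR PR CR PD | CR | 4 | SD | PR |
| PR CR NE | CR | 5 | SD | PR |
| PR CR SD | CR | 3 | SD | PR |
| PR CR PR | CR | 2 | SD, PD or PR | PR |
| PR CR (last scan) | CR | 14 | unclear | PR |
| PR CR CR | first CR | 1 | CR | CR |
| PR SD PR | first PR | PR by footnote ** | PR | PR |
| PR NE PR | first PR | PR by footnote ** | PR | PR |

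**The 35-day condition.** A CR that confirms a PR comes at least 28 days after it. For that CR to fall before day 35, the PR would have to fall before day 35 − 28 = 7. On the 6-weekly schedule the earliest such CR is at about day 84, so the SD branch of cases 3 to 5 applies.

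**CBR.** SAP 8.4.3 requires SD of at least 182 days but gives no start and end dates for SD. Taking SD from randomization to PD (an assumption):

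- PR CR PD: 3 × 42 = 126 days, below 182, so clinical benefit is lost.
- PR PR CR PD: 4 × 42 = 168 days, lost.
- PR PR PR CR PD: 5 × 42 = 210 days, kept.

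If SD instead ended at the last scan without PD, the third sequence would have 4 × 42 = 168 days and would be lost as well.

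**DCR.** SAP 8.4.4 counts SD of any duration, so DCR does not change where the output is SD.

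**The case against.** The best defence is that the appendix already shows what was meant. Rule (a), rule (c), case 6 and the closing sentence all point to a review of every assessment, as does protocol Table 17, and a reading that gives case 6 any effect produces the right answer. That is probably the intention. But these statements conflict with step (d) without overriding it, and nothing in the available text sends the programmer back to an earlier PR.

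Second, the start of rule (b) and note (3) to case 8 are missing from the available text, and rule (b) concerns the first time point response. They might deal with an earlier PR. The surviving end of rule (b) repeats the CR-first order, which makes that less likely, but the finding has to be limited to the text available.

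Third, case 2 and note (a) to Table 17 treat disease seen after a true CR as progression. This makes sequences with SD after the CR less clean than those with PD or NE. It does not cancel a PR confirmed earlier, and PR CR PD, PR PR CR PD and PR CR NE do not depend on it.

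Fourth, case 14 exempts patients who qualify for CR or PR. A reader might count PR CR with no later scan as a definite error. The wording there is ambiguous, so it is not counted as one. Cases 3 to 5 carry no such exemption.

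A reader might also infer that the co-primary ORR is affected. It is not: SAP 8.1.2 bases it on the IRC assessment, and Appendix 14.5 is for the local investigator's review.

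**Conclusion.** The point holds on the available text. Step (d) makes case 6 unreachable and records an already confirmed PR as SD when the first CR is followed by PD or by NE that is not resolved. The same output follows when SD comes after the CR, subject to the reservation about case 2 and note (a).

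The consequence is limited. Investigator-assessed ORR, time to response, duration of response and some CBR results can change. SAP 8.4 calls these analyses supportive and places them outside Type I error control.

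A reader might infer a bias of known size, or one that favours an arm. The documents support neither, because they do not say how often an investigator PR is followed by an unconfirmed CR in either arm. The number affected could be zero. Counting the possible response patterns would not help, since patterns are not patient frequencies.

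The conclusion assumes that the missing parts of rule (b) and note (3) contain no instruction to return to an earlier PR. The CBR examples also rest on the assumed dating of SD.

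**What to change.** Reword step (d) so that every assessment before first PD or new anti-cancer therapy may be the first of a confirming pair, and best response is the highest response confirmed:

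- CR if a CR is confirmed by a CR;
- otherwise PR if a PR is confirmed by a PR or CR;
- otherwise SD, PD or NE by the 35-day rule.

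Keep the existing limits explicit. A pair must be consecutive assessments at least 28 days apart, with only the gaps in footnote **: up to three intervening NEs, and one intervening SD between PRs only. So CR SD CR is not a confirmed CR, and neither PR SD NE PR nor PR NE NE NE NE PR is a confirmed PR. In the available text, one PR example in SAP Section 12 shows four NEs beside a stated limit of three; check it and align it with the footnote.

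Then state four things:

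1. Whether the NE allowance also covers PR NE CR.
2. A PR confirmed before or at the first CR is kept whatever follows that CR, so PR PR CR PR is PR.
3. Case 2 and Table 17 note (a) apply only when no PR was confirmed by then, so CR PR stays in case 2 and PR SD CR PD stays SD.
4. Case 14 records PR for a patient who already qualifies for PR.

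The cost is appendix wording and derivation code. No new data are needed.
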